- **Study Design:** A randomized, double-blind, placebo-controlled, parallel-group study of flexible dose mixed salts amphetamine (5-60 mg) adjunctive to antidepressant therapy among adult outpatients with major depressive disorder responding inadequately to current antidepressant therapy.

Fig. 1: Treatment Groups

Visit	Phase	Weeks	Group	Group	Procedures
		on med	1	2	
V1		Scr			Inclusion/Exclusion
V2		0			Baseline measurement + disp.
V3	Ι	1	MSA	PBO	Measure effect of 1 week on study med + disp.
V4	Ι	2	MSA	PBO	Measure effect of 2 weeks on study med + disp.
V5	Ι	3	MSA	PBO	Measure effect of 3 weeks on study med + disp.
V6	II	4	MSA	MSA	Measure effect of 3 weeks on study med + disp.
V7	II	5	MSA	MSA	Measure effect of 3 weeks on study med + disp.
V8	II	6	MSA	MSA	Measure effect of 3 weeks on study med
V9		(8)			Safety follow-up

Fig. 2: Study Design Overview

The treatment phase of the study consists of 2 phases (21 treatment days per phase). Study Phase 1 will consist of visits 2 (baseline) through 5. Study Phase 2 will consist of visits 6 through 8. There will be a follow-up visit 2 weeks following visit 8. There is a one-week interval between study visits, with a scheduling window of \pm 3 days allowed.

Mixed salts amphetamine is FDA-approved for Attention Deficit-Hyperactivity Disorder (ADHD) and superior in efficacy to placebo; therefore, comorbid ADHD will be statistically controlled as a continuously-variable covariate, but will not be considered an exclusionary condition.

The primary analysis will be a repeated measures analysis of variance using a mixed-effects model (PROC MIXED-MMRM). The primary outcome measure will be the MGH-CPFQ total score at baseline and the MGH-CPFQ total score at the end of the trial. The independent variables will be the study visit, the treatment in the previous phase, and treatment assignment. The variance covariance matrix for the repeated measures will be unspecified.

Enrollment Period: The enrollment period is estimated to be 6 months. The last patient is expected to complete the study by March 31, 2010.

Number of Subjects: 40 subjects will be randomized (20 to each treatment arm). Additional subjects may be consented to allow for screen failures. Subjects who terminate early post-randomization will be replaced only sufficiently to ensure a total number of 24 (12 to each treatment arm) evaluable subjects.

Duration of Subjects' Study Participation: There will be a total of 9 study visits over a period of 9 weeks.

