- 11) Pregnant or breastfeeding women.

Study Procedures: Figure 3 shows study procedures to be performed at each visit. No study procedures will be performed until a subject signs the informed consent document.

Screen visit (Visit 1): Medical and psychiatric history will be taken, a physical examination and vital signs will be performed and lab tests done. Lab tests include CBC, CMP, urine drug screen and urine pregnancy test for females of childbearing potential. If a subject has had the required lab tests performed within the past 3 months and can produce the results, lab procedures may be waived at the screening visit for that patient (except urine pregnancy test). The HDRS-17 score upon screening will be used to determine entry eligibility (see inclusion criteria). Beyond the patient's verbal report, we will attempt to obtain medical records (e.g., previous clinician or pharmacy records) to document adequate dose and duration of previous/current ADT.

Study Phase 1

Baseline visit (Visit 2): Screened and eligible subjects will return one week after the screening visit. At this visit (provided entry criteria continue to be met) subjects will be randomized in double-blind fashion to one of two treatment groups:

- Group 1: MSA during both phases; or
- Group 2: PBO during Phase 1 followed by MSA during phase 2

Study drug will be dispensed to the subject in sufficient quantity to last until the next study visit (7 days +/-3).

Study visits 3-5: Following the baseline visit, subjects will return at one-week intervals for study visits 3-5. Study procedures to be performed are reflected in Figure 3. Phase 2 study drug is dispensed at study visit 5.

Study visits 6-8: Subjects will return at one-week intervals for study visits 6-8. Study procedures to be performed are reflected in Figure 3. At visit 8, all subjects will receive instructions for tapering the dose of the MSA to avoid potential difficulties from abrupt discontinuation of the study drug.

Study visit 9: Subjects will return two weeks following visit 8 for a safety follow-up check. Procedures to be performed are reflected in Figure 3.

If a subject withdraws or is terminated early from the study, visit 9 procedures will be performed at the final study visit.

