All concomitant medications taken during the study will be recorded in the case report form, along with dosage information and start and stop dates. Subjects requiring excluded drugs will be discontinued from the study. Medication management and clinical ratings will be performed by the study clinicians.

Subjects who complete the trial will be offered referrals to qualified physicians for the purposes of continued care. At the conclusion of Visit 8, study blind will be removed by an unblinded study staff member for facilitation of ongoing treatment by patient's selected follow-up care provider. At Visit 8, study subjects will be provided a one-month prescription for the dose of MSA they are currently prescribed in the study to ease transition to their follow-up care physician.

At the end of the study, subjects will be followed for up to three months while an appointment can be secured with their original treatment provider or with one referred by the research center.

Investigational Product(s), Dose and Mode of Administration, Duration of Treatment with Investigational Product(s): Based upon clinical judgment and ascertained between clinician and patient, study drug will be dosed as follows: The total daily dosage of study drug will be 5-60 mg, supplied in 5 and 10 mg tablets of MSA or matching PBO.

Total daily dosing of the concurrent ADT will be as follows: escitalopram 10-40 mg; fluoxetine 20-80 mg; paroxetine CR 25-100 mg (paroxetine 20-80 mg may be substituted if paroxetine CR is not available); sertraline 100-400 mg; venlafaxine XR 150-600 mg; desvenlafaxine 50-200mg; citalopram 20-80 mg; or duloxetine 60-180 mg; bupropion 150-450 mg; mirtazapine 15-45 mg, tricyclics (standard dosing, individually per label instructions).

The dose of MSA begins at 5mg BID. MSA dose range will be 5mg-20mg BID or TID, not to exceed 60mg per day in addition to the stable dose of ongoing ADT. Each study medication tablet will be 5 or 10 mg of MSA or PBO. Upward titration will be based upon physician's clinical judgment and confirmed by patient's consent.

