Study Assessments and Primary Endpoints: The difference in absolute change in score from baseline to endpoint in the MGH-CPFQ between the MSA and the PBO groups is the primary endpoint. Key secondary endpoints will be difference in absolute change from baseline in MADRS score between MSA and PBO, difference in remission rates (MADRS < 11) between MSA and PBO, the change from baseline in total score at endpoint of MGH-CPFQ item analysis, difference in change scores on the CGI-S, CGI-I and QIDS. Safety outcome measures: adverse events, physical examinations, vital signs; blood pressure, orthostatic; EKG; Rush Sexual Inventory (RSI).

Statistical Methods: The randomized sample includes all patients who are randomized. The Safety sample will include those randomized patients who received at least one dose of doubleblind study medication as indicated on the dosing record. The efficacy sample will include those patients in the safety sample who have at least one efficacy evaluation post-randomization. The last observation carried forward (LOCF) data set includes data recorded at a given visit after randomization, or, if no observation is recorded at that visit, data carried forward from the previous postrandomization visit. The LOCF data set is primary, and analysis of the observed case data set also will be conducted.

The primary analysis will compare pooled MGH-CPFQ response rates between PBO and MSA and PBO non-responders. Differences in response rates will be compared using the CMH General Association Test. Descriptive statistics on non-primary groups will be conducted.

This study seeks to estimate the strength of any statistically significant relationship, or effect size, in addition to statistical significance of found treatment effects.

Secondary Endpoints Analysis: Differences in remission (defined as an endpoint MADRS score <11) rates will be compared using the CMH General Association Test. Logistic regression analysis will be performed to explore the relationship between response and patients' demographics and prognostic variables including baseline QIDS score, gender, site, and age, etc. Similar analyses will be performed for remission.

Fig. 3	: Stud	y Proce	dures	Table
--------	--------	---------	-------	-------

			Treatment period 1			Treatment period 2			
Study Visit	V1 Screen	V2 Baseline	V3	V4	V5	V6	V7	V8	V9 F/UP
End of Week	-1	0	1	2	3	4	5	6	8
Day	-7	0	7	14	21	28	35	42	56
Informed consent	Х								
Demographic data	Х								

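### The primary model places its outcome at a time when both groups take MSA, and it names no visit or contrast for the MSA-versus-placebo comparison

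*Combined protocol and SAP*

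**What the plan says.** The question itself is clear. The Research Hypotheses compare MSA with placebo on CPFQ change, and the Statistical Analysis section gives the primary endpoint as: "The difference in absolute change in score from baseline to endpoint in the MGH-CPFQ between the MSA and the PBO groups". Neither place says which visit is the endpoint.

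The primary analysis paragraph of Study Design does put a time on it: "The primary outcome measure will be the MGH-CPFQ total score at baseline and the MGH-CPFQ total score at the end of the trial". Fig. 3 schedules the last CPFQ at Visit 8. The model terms follow: "The independent variables will be the study visit, the treatment in the previous phase, and treatment assignment". On covariance: "The variance covariance matrix for the repeated measures will be unspecified".

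Fig. 1 and the Baseline visit text fix the treatments. Group 1 takes MSA throughout. The other arm is "Group 2: PBO during Phase 1 followed by MSA during phase 2". Phase 2 is Visits 6–8, so Visit 5 is the last placebo-controlled assessment.

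Statistical Methods then describes a different main analysis: "The primary analysis will compare pooled MGH-CPFQ response rates between PBO and MSA and PBO non-responders". It uses a CMH test, and adds: "The LOCF data set is primary, and analysis of the observed case data set also will be conducted". Neither statement supplies a contrast visit for the mixed model.

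**The concern.** At Visit 8 Group 1 has had six weeks of MSA and Group 2 three. A difference there answers a question about duration or delayed start, not MSA versus placebo. If Group 2 catches up in Phase 2, an effective drug would show little or nothing at the stated endpoint.

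The model could still recover the placebo comparison from Phase 1 data. That depends on three things the plan leaves open: which visits form the outcome rows, whether treatment assignment means the randomised group or the treatment being taken at the time, and which coefficient or visit is the primary contrast. Baseline CPFQ is part of the outcome, so a baseline covariate is not strictly required. But a difference in change then needs a treatment-by-visit term or equivalent coding, and none is listed. Two analysts following the same paragraph could report different treatment effects.

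**Working it through.** **Inputs from the documents.** Phase 1 is Visits 2–5 and Phase 2 is Visits 6–8 (Study Design). Treatments are from Fig. 1, and CPFQ is collected at Visits 2–8 (Fig. 3). There are 20 randomised per arm, with at least 12 per arm evaluable. No alpha, power, SD or effect size is given, so the plan has no figure of its own to reproduce here.

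**Assumptions.** SD 1; equal arms; correlation 0.4–0.8, either compound symmetry (CS) or AR(1). Group differences at Visits 3–8: rising 0.5, 0.8, 1.0, 0.5, 0.2, 0; flat 1, 1, 1, 0.5, 0.2, 0. The Visit 3–5 averages are (0.5 + 0.8 + 1.0)/3 = 0.767 and 1.

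**Model.** Mean = visit effect + γP + τT. P = 1 for Group 1 in Phase 2 and 0 otherwise. T is either the randomised group or the current treatment (0 for everyone at baseline). D_v is the Group 1 minus Group 2 difference at visit v; D_2 has expectation 0 by randomisation.

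**Visits 2 and 8.** Group coding: D_2 = τ and D_8 = τ + γ, so τ is the baseline difference (expected 0) and γ = D_8 − D_2. Current-treatment coding: both groups have T = 0 at Visit 2 and T = 1 at Visit 8, so τ is aliased with visit (rank 3 of 4). What remains is six versus three weeks of MSA.

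**Visits 5 and 8.** Group coding: D_5 = τ and D_8 = τ + γ. Current-treatment coding: D_5 = τ and D_8 = γ. Both give exactly τ = D_5. Adding Visit 2 leaves D_5 under current-treatment coding but gives (0 + D_5)/2 under group coding.

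**Visits 3–8.** Both codings give the same τ, a weighted sum of the D_v.
- CS: weights 1/3, 1/3, 1/3, 0, 0, 0, which is the Visit 3–5 average.
- AR(1) 0.8: weights 0.410, 0.082, 0.508, −0.365, 0.061, 0.304.
  - Flat: 1.000 − 0.365 × 0.5 + 0.061 × 0.2 = 0.830, or 83% of the average.
  - Rising: 0.205 + 0.066 + 0.508 − 0.183 + 0.012 = 0.608, or 0.608/0.767 = 79%.
- AR(1) 0.4: 0.942 flat (94%) and 0.713 rising (93%).
- The Phase 2 weights sum to zero, so a constant Phase 2 difference cancels. With 0.5 at Visits 6–8, τ is 1.000 (flat) or 0.767–0.778 (rising).

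**Visits 2–8.** τ by coding:

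| Coding | Profile | CS | AR(1) 0.4–0.8 | Share of Visit 3–5 average |
|---|---|---|---|---|
| Group | rising | 0.575 | 0.410–0.523 | 53–75% |
| Group | flat | 0.750 | 0.463–0.650 | 46–75% |
| Current | rising | 0.767 | 0.547–0.694 | 71–100% |
| Current | flat | 1.000 | 0.916–0.947 | 92–100% |

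Under CS the group-coding loss is simply (0 + D_3 + D_4 + D_5)/4, three quarters of the average.

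**Power of the Visit 8 change contrast.** Two-sided 5%, 20 per arm, assumed Phase 1 effect 0.8 SD, SE = √(2(1 − r) × 2/20). For r = 0.4, SE = 0.346; for r = 0.8, SE = 0.200. Power is 61–97% if the whole difference is still present at Visit 8, 20–50% if half remains, 9–16% if a quarter remains, and 5% if none.

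**Precision of the two candidate contrasts, baseline-adjusted.** Under CS the SE ratio of Visit 5 to the Visit 3–5 average is √(3(1 + r)/(1 + 3r)): 1.38 at r = 0.4 and 1.26 at r = 0.8. Under AR(1) it is 1.34–1.41. Signal-to-noise of Visit 5 relative to the average, rising profile: (1/0.767)/1.41 = 0.93 to (1/0.767)/1.26 = 1.03. Flat profile: 1/1.41 = 0.71 to 1/1.26 = 0.79.

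**The case against.** The strongest reply is that the previous-phase term shows the sponsor had a two-phase, time-varying model in mind. On that view the natural rows are the phase ends, Visits 5 and 8, and the treatment coefficient is then exactly the Visit 5 placebo-controlled difference under either coding. This stands. A reader might infer that the listed terms can never give an MSA-versus-placebo estimate, and the documents do not support that. But the plan does not state the phase-end reading, and it conflicts with the sentence that sets the outcome at baseline and trial end.

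Three other stronger readings also go too far.
- A reader might conclude that using all post-baseline visits dilutes the effect. That needs both a decaying correlation and a Phase 2 difference that changes over visits. Under CS there is no loss, and with a constant Phase 2 difference there is essentially none.
- A reader might take the covariance sentence as leaving the structure to the analyst. If the word means unstructured, which is likely, the structure is prespecified and is not itself a defect.
- A reader might say baseline is ignored. It is part of the outcome; what is absent is a baseline CPFQ covariate or a treatment-by-visit term.

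The CMH and LOCF text is a separate inconsistency. It adds a competing primary analysis but does not cause the missing contrast.

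**Conclusion.** The point holds. As written, the outcome time and the stated MSA-versus-placebo endpoint cannot both be met, because no group is on placebo after Visit 5. The listed terms do not say which Phase 1 comparison is meant instead. Depending on the reading, the treatment coefficient is expected to be zero, is not estimable, equals the Visit 5 difference or half of it, or is a weighted average. That weighted average runs from about 46% of the Visit 3–5 average to the whole of it.

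The zero, not-estimable, Visit 5 and half-of-Visit 5 results follow from the design and from randomisation alone. The other percentages and the power figures rest on assumed effect profiles, correlations and effect size, since the documents give none. The plan should be corrected, but valid readings do exist, so this is a failure to specify the analysis and not proof that the trial cannot answer its question.

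**What to change.** Replace the end-of-trial outcome with one contrast in the placebo-controlled phase, and say openly that it is a replacement. Model CPFQ change at Visits 3–5 on baseline CPFQ, visit, treatment and treatment-by-visit, with unstructured covariance. Name either Visit 5 or the Visit 3–5 average as the single primary contrast; both are legitimate. Drop the previous-phase term from the primary model and report Visits 6–8 as secondary. State whether this model or the CMH response-rate analysis is primary, and make the other supportive.

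Costs: no new visits or scales, since CPFQ is already collected at Visits 2–5. Phase 2 data leave the primary analysis, and baseline uses one degree of freedom. Choosing Visit 5 means a standard error 26–41% larger than for the average. Its signal-to-noise is about equal if the effect rises (0.93–1.03) and lower if it is flat. In return, an unstructured covariance needs 3 × 4/2 = 6 parameters, against 6 × 7/2 = 21 for Visits 3–8 or 7 × 8/2 = 28 for Visits 2–8, with 24–40 subjects.

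Date the amendment before anyone involved in the analysis sees outcomes by arm. The plan says: "At the conclusion of Visit 8, study blind will be removed by an unblinded study staff member". It does not say analysts see the codes then, so amending before the first such unblinding is the safest point, not a strict requirement of the text.

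A separate minor item: Study Design promises a continuous ADHD covariate, but it is not among the model terms and Fig. 3 lists no ADHD scale. These places should be reconciled.

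### The primary mixed model contains a previous-phase treatment term that is blank in Phase 1 and duplicates the randomised group in Phase 2, so on the outcome values named the treatment test is either not estimable or a test of baseline scores

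*Combined protocol and SAP*

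**What the plan says.** The Study Design section names a repeated-measures mixed model (PROC MIXED, MMRM) as the primary analysis. On the outcome it says: "The primary outcome measure will be the MGH-CPFQ total score at baseline and the MGH-CPFQ total score at the end of the trial". On the fixed effects: "The independent variables will be the study visit, the treatment in the previous phase, and treatment assignment". On the covariance: "The variance covariance matrix for the repeated measures will be unspecified", which I take to mean unstructured. It names no visit-by-treatment interaction. Comorbid ADHD is to be a continuous covariate.

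The same section defines two phases: "Study Phase 1 will consist of visits 2 (baseline) through 5" and "Study Phase 2 will consist of visits 6 through 8". The Baseline visit (Visit 2) paragraph describes a single randomisation. Group 1 takes MSA in both phases; the other arm is "Group 2: PBO during Phase 1 followed by MSA during phase 2". Fig. 1 shows both groups on MSA at Visits 6 to 8, and Fig. 3 schedules the MGH-CPFQ at every visit from 1 to 8.

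The Statistical Analysis section gives the primary endpoint as the MSA-placebo difference in change from baseline to endpoint. Its Statistical Methods paragraph then describes a different primary analysis, a CMH comparison of response rates. No passage says how previous-phase treatment is coded in Phase 1.

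**The concern.** A previous-phase term belongs to a crossover or re-randomised design, where it can differ from the current assignment. Here there is one randomisation and no phase before Phase 1, so the term adds nothing to group and visit. In Phase 1 it has no value, and in Phase 2 it is the randomised group under another name.

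The model that carries the trial's main conclusion may then fail to estimate a treatment effect. Worse, it may print an ordinary-looking p-value labelled treatment assignment that concerns scores taken before any study drug. Which of these happens depends on a coding choice that the plan leaves to the programmer.

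**Working it through.** The plan states no figure for this point, so there is none to reproduce. The check is algebraic.

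**Inputs.** Phases, visits and sequences come from the Study Design section and the Baseline visit paragraph. 'End of the trial' is read as Visit 8, the last treatment visit. The ADHD covariate is left out because it does not remove the aliasing.

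**Model.** For group *g* (M = MSA-MSA, P = placebo-MSA) at visit *t*, the mean is μ + v(t) + p(previous-phase treatment) + a(assignment). Let D2 and D8 be the group differences (M minus P) at Visits 2 and 8.

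**Rows at Visits 2 and 8**

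1. *Blank treated as missing.* Visit 2 rows are dropped. With assignment = randomised group, the one remaining equation is D8 = [p(M) − p(P)] + [a(M) − a(P)]. It has two unknowns, so assignment given the other terms has 0 df.
2. *Blank coded 'none', assignment = randomised group.* At Visit 2 both groups share p(none), so D2 = a(M) − a(P). At Visit 8, D8 = [p(M) − p(P)] + [a(M) − a(P)]. Hence assignment = D2 and previous-phase = D8 − D2. The design has rank 4 for 4 cells. The assignment weights are +1 and −1 on the two Visit 2 cells and 0 on Visit 8.
3. *Blank coded 'none', assignment = current drug, with no drug at Visit 2.* Everyone has no drug at Visit 2 and MSA at Visit 8, so assignment duplicates visit: rank 3, 0 df. If Visit 2 is instead labelled with the Phase 1 drug, assignment is D2 again.

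**Other row sets** (unweighted least-squares weights)

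| Rows | Blank in Phase 1 | Assignment | df for assignment | What it estimates |
|---|---|---|---|---|
| Visits 2-8 | missing | either reading | 0 | nothing; 8 of 14 group-by-visit cells are dropped |
| Visits 2-8 | 'none' | randomised group | 1 | 1/4 on each of the Visit 2, 3, 4 and 5 differences |
| Visits 2-8 | 'none' | current drug, none at Visit 2 | 1 | 1/3 on each of the Visit 3, 4 and 5 differences |
| Visits 3-8 | 'none' | either reading | 1 | 1/3 on each of the Visit 3, 4 and 5 differences |
| Visits 3-5 | missing | either reading | no rows left | nothing |
| Visits 3-5 | 'none' | either reading | 1 | 1/3 on each of the Visit 3, 4 and 5 differences; the previous-phase term is constant |

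**Simulation of case 2.** This used 20 per arm, as planned, and an unstructured covariance. The means (28 and 24), variances (36 and 49) and covariance (18) are assumptions; the ranks and the case 2 identities do not depend on them. In one simulated data set the assignment coefficient was −1.212, equal to D2, for true end-of-trial effects of 0, −5 and −10. The previous-phase coefficients were 1.464, −3.536 and −8.536. Over 4,000 runs:

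| True end-of-trial effect | Rejections on assignment | Rejections on previous phase |
|---|---|---|
| 0 | 5.3% | 4.7% |
| −5 | 5.3% | 62.7% |
| −10 | 5.3% | 99.4% |

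**Deleting the term and changing nothing else.** With Visit 2 and Visit 8 rows, group as a main effect and no interaction, the group coefficient is a weighted average of D2 and D8. Under the assumed covariance the weight on D2 is (49 − 18)/(36 + 49 − 2×18) = 31/49 = 0.63, and on D8 it is 18/49 = 0.37. For the −5 data set, 0.633×(−1.212) + 0.367×(−4.748) = −2.51, which matches the fitted −2.511. That is neither a change from baseline nor a comparison with placebo.

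**The case against.** The best reply is that the sentence on the outcome measure does not list the records entering the model, and does not say Visit 8. A repeated-measures model with visit as a factor, and an outcome collected at every visit, can fairly be read as using all visits. If Phase 1 is then given its own level, assignment is estimable. If assignment means current drug, with none at Visit 2, it averages exactly the placebo-controlled differences at Visits 3 to 5, and the previous-phase term absorbs the Phase 2 difference. That reply stands. A reader might infer that the model fails on every reading, or that no interaction or Visit 5 contrast could work while the term remains. The documents do not support either. With the 'none' level and Phase 1 rows included, a Visit 5 contrast is estimable, and on Phase 1 rows alone the term is a harmless constant.

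But the plan states neither the all-visit data set nor the extra level. If the blank is left missing, the all-visit model loses every placebo-controlled observation.

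Two further replies are weaker. Under case 2 the change contrast does survive, in the previous-phase term; but at Visit 8 that compares six with three weeks of MSA, not MSA with placebo. One other coding (own group as previous phase at baseline, and the Phase 1 drug as current drug there) makes assignment a difference in change with the sign reversed. It contradicts the meaning of a previous phase and again compares the two sequences at Visit 8.

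Finally, the CMH analysis in Statistical Methods leaves it unsettled whether this model is primary. It neither defines nor withdraws the term.

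**Conclusion.** The primary model is wrong as written and should be corrected before analysis. On baseline and end-of-trial values, taken as Visits 2 and 8, treatment assignment has 0 df, or is exactly the pre-dose difference, under every coding consistent with the meaning of the term. With all visits it has 0 df if the blank is missing. It becomes estimable once an unstated level is added, with a quarter of the unweighted weight on baseline if Visit 2 is modelled and assignment is the randomised group.

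The algebra rests on two phases, one randomisation and no stated interaction, all taken from the plan. The reading of the end of the trial as Visit 8 is an inference, though the natural one. The rejection rates rest on assumed means and covariance.

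A reader might also infer that striking the phrase is enough. It is not: the remaining main effect would mix baseline with a visit at which both groups take MSA. Nor does the point imply that the trial cannot answer its question, because Visits 3 to 5 hold a valid randomised placebo comparison.

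**What to change.** 1. Delete the previous-phase treatment term from the primary model.
2. Fit the model to Visits 3 to 5 with baseline MGH-CPFQ, visit, randomised group and visit-by-group, plus the ADHD covariate already planned. Name the covariance as unstructured. Make the group contrast at Visit 5 the primary test.
3. Analyse Visits 6 to 8 in a separate descriptive model with randomised sequence (MSA-MSA or placebo-MSA) as the only group term.
4. State whether this model replaces the CMH response-rate analysis in Statistical Methods or how the two rank, so that one primary analysis remains.

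The cost is edits to the analysis text. Fig. 3 already schedules the MGH-CPFQ at every visit needed, so no data collection or operations change. The substantive consequence is that the primary comparison is at week 3, the last visit at which Group 2 has had only placebo, and not at week 6.

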- 1. Primary outcome: The group treated with MSA adjunctive to ADT will show a greater mean change from baseline to endpoint in total score as compared to the group treated with placebo (PBO) adjunctive to ADT as measured by the
 - a. Massachusetts General Hospital Cognitive-Physical Function Questionnaire (MGH-CPFQ)
- 2. Secondary outcome:
 - a. MSA adjunctive to ADT will demonstrate clinically acceptable safety and tolerability, compared to placebo, based on
 - i. spontaneously reported adverse events and significant adverse events
 - ii. significant changes in blood pressure and pulse
 - iii. significant changes in weight
 - iv. significant changes in electrocardiogram
 - v. significant changes in the Rush Sexual Inventory
 - b. The group treated with MSA adjunctive to ADT will show a greater mean change from baseline to endpoint as compared to the group treated with PBO adjunctive to ADT as measured by the change on
 - i. MGH-CPFQ individual item analysis
 - ii. MADRS scores:
 - 1. Total score
 - 2. Subscales
 - 3. Individual item analysis
 - 4. Percent of "responders" (\geq 50% reduction in score baseline to endpoint)
 - 5. Percent reaching "remission" (score of ≤ 10 at endpoint)

- c. The group treated with MSA adjunctive to ADT will show statistically significant improvement in core residual symptoms of MDD extant on monotherapy ADT as measured by the
 - i. PGI (Patient Impression and Improvement) scales
 - ii. Quick Inventory of Depressive Symptomatology-16 (QIDS-16) total score (≤ 6) and subscale
 - iii. Clinical Global Impression-Severity (CGI-S); and, Clinical Global Impression-Improvement (CGI-I)
 - iv. QIDS total score and subscale
- d. The group treated with MSA adjunctive to ADT will show statistically significantly improvement in overall functioning (work, social and cognitive) when compared to the group treated with PBO and ADT as measured by the
 - i. Total and individual item scores from the HDRS-17 and -28
 - ii. Maier and other subscale scores from the HDRS-17 and -28
 - iii. Scale For Assessment Of Negative Symptoms (SANS)
 - iv. Health Status Questionnaire, 2nd ed. (HSQ 2.0)
 - v. SF-36 Health Survey (SF36)
 - vi. Fawcett Experienced Pleasure Index (EPI)
 - vii. Endicott Work Productivity Scale (EWPS)
 - viii. Sheehan Disability Scale (SDS)
 - ix. Fatigue Associated with Symptoms of Depression (FASD)

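### Fitted as listed with default standard errors, the repeated-measures model rejects too often: about 8% at 40 subjects and 11% at the 24-subject floor, against an assumed 5%

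*Combined protocol and SAP*

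**What the plan says.** The Study Design section of the combined protocol and SAP calls the primary analysis a mixed-effects repeated-measures model in PROC MIXED. On the terms: "The independent variables will be the study visit, the treatment in the previous phase, and treatment assignment". On the covariance: "The variance covariance matrix for the repeated measures will be unspecified". No interaction, degrees-of-freedom method or standard-error method is given there or under Statistical Analysis.

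The same paragraph describes the outcome as the baseline and end-of-trial MGH-CPFQ totals, although Fig. 3 collects the scale at every visit from V1 to V8. Number of Subjects randomizes 40, 20 per arm, and replaces early terminators only as far as needed to keep "24 (12 to each treatment arm) evaluable subjects".

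The primary hypothesis is that the MSA group "will show a greater mean change from baseline to endpoint in total score". Statistical Methods makes the LOCF data set primary and names a different primary analysis: MGH-CPFQ response rates compared by a CMH test.

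**The concern.** An unstructured matrix over six visits has 6 × 7 / 2 = 21 parameters, to be estimated from 24 to 40 people. With main effects only, the treatment coefficient is a weighted average over visits, and the weights come from that estimated matrix. The ordinary model-based standard error treats the matrix as known. It therefore leaves out the extra variability from estimating the weights, and the residual variance it uses is also too small on average.

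If this model carries the primary efficacy claim, its confidence interval is too narrow and its p-value too small. A program written from this text would contain no instruction to correct either.

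**Working it through.** The plan gives no alpha, power or sample-size figure to reproduce, so the check asks what error rate the listed model delivers.

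**Inputs**
- Level: two-sided 5%, assumed. Statistical Methods mentions an effect size "in addition to statistical significance of found treatment effects" but gives no level or sidedness.
- N: 40 randomized 1:1, with a floor of 24 evaluable (Number of Subjects).
- T, the time points modelled: 6 for V3-V8, 3 for the Phase 1 visits V3-V5, or 2 if only the baseline and end-of-trial scores are used.
- q, the treatment parameters: 1 for a single treatment coefficient; 2 when the previous-phase term is a separate coefficient (in Phase 2 everyone takes MSA, so that term carries the arm difference there); T with a visit-by-treatment term.
- Reference distribution: t with N − 2 degrees of freedom, assumed.

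**Formulas** (complete data, REML, unstructured matrix, a free mean at each visit). Let k = T − q and ν = N − 2. Up to a common factor:
- reported variance = χ²(ν − k) / ν, with mean (ν − k) / ν;
- true variance = 1 + χ²(k) / χ²(ν − k + 1), with mean 1 + k / (ν − k − 1);
- SE ratio = √[mean reported variance / mean true variance].

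Neither expression depends on the true covariance, so the choice of correlation pattern does not drive the result.

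**Listed terms, V3-V8 (T = 6, q = 2, k = 4)**
- N = 24, ν = 22: reported 18/22 = 0.818; true 1 + 4/17 = 1.235; ratio √(0.818/1.235) = 0.814.
- N = 40, ν = 38: reported 34/38 = 0.895; true 1 + 4/33 = 1.121; ratio √(0.895/1.121) = 0.893.

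Rejection rates come from 400,000 draws per case, dividing a normal variable scaled by the true variance by the reported standard error:

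| Reading | k | SE ratio, N=24 | Type I error, N=24 | SE ratio, N=40 | Type I error, N=40 |
|---|---|---|---|---|---|
| V3-V8, treatment and previous-phase terms | 4 | 0.814 | 10.9% | 0.893 | 7.9% |
| V3-V8, treatment term only | 5 | 0.767 | 13.0% | 0.867 | 8.9% |
| V3-V5, treatment term only | 2 | 0.907 | 7.5% | 0.947 | 6.3% |
| Baseline and end of trial only | 1 | 0.953 | 6.2% | 0.973 | 5.7% |
| Visit-by-treatment, final-visit contrast | 0 | 1.000 | 5.0% | 1.000 | 5.0% |

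**Check by full REML fits** to simulated null data (AR(1), correlation 0.6):
- V3-V8, treatment term only: 12.6% at N = 24 and 8.6% at N = 40.
- V3-V5, treatment term only: 7.9% at N = 24.
- V3-V8 with the previous-phase term: 12.4% at N = 24. This rests on 850 data sets (Monte Carlo SE 1.1 points) and is compatible with 10.9%.
- Six-visit visit-by-treatment model: 5.5% at N = 24 (Monte Carlo SE 0.7 points).

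**Kenward-Roger-type correction alone, treatment term only:** 7.0% (N = 24, six visits), 6.4% (N = 24, three visits) and 5.5% (N = 40, six visits), with Monte Carlo SE about 0.6-0.7 points. At 24 subjects the correction does not fully restore 5% while the treatment effect stays averaged over visits.

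**The case against.** A reader might infer that this trial's primary test is known to run at 7-13%. The documents do not support that, for these reasons:

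- No alpha or sidedness is stated, and silence about the standard-error method is an omission, not a decision against correction.
- Reading the covariance statement as unstructured is natural but is still a reading.
- The outcome sentence names only two scores, which gives about 6%.
- A list of independent variables does not exclude an interaction, and the change-to-endpoint hypothesis calls for one. With it, the rate is 5.0% on complete data.
- The 13% figure needs 24 subjects and omits a listed term. Twenty-four is a floor: the efficacy sample takes any dosed subject with one post-randomization evaluation, and LOCF fills the gaps, so the fit may hold close to 40.
- The calculations use complete data. They do not examine LOCF or include the continuous ADHD covariate that Study Design mentions outside its list of terms.
- The inflation does not touch the CMH comparison that Statistical Methods calls primary.

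All of this stands, and it makes the finding conditional. It does not remove it. A previous-phase term has content only if Phase 2 visits are in the model, so the six-visit reading is at least as natural as the two-score one. Every main-effects reading in the table lies above 5%.

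**Conclusion.** The concern holds conditionally. If the model is fitted with the listed main effects, an unstructured matrix and default model-based standard errors, the reported standard error over V3-V8 averages about 11% below the true one at N = 40 and 19% below it at N = 24. A nominal two-sided 5% test then rejects a true null about 8% and 11% of the time. The full span over readings and sample sizes is about 6% to 13%, with the top requiring the 24-subject floor and no previous-phase term.

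These figures assume a two-sided 5% level, complete data and N − 2 degrees of freedom. They concern the mixed model only. The disagreement between Study Design and Statistical Methods over which analysis is primary is a separate matter that the sponsor has to settle.

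**What to change.** In the Study Design analysis paragraph:

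1. Specify Kenward-Roger standard errors and degrees of freedom (DDFM=KR).
2. Fit the placebo-controlled Phase 1 visits V3-V5 (3 × 4 / 2 = 6 covariance parameters) with a visit-by-treatment term, and name the V5 treatment contrast as the primary test. Both this and step 1 are needed: the contrast brings the rate to 5.0% on complete data, which the correction alone does not do at N = 24.
3. Drop the previous-phase term, which is empty in Phase 1, and say whether the ADHD covariate is in the model.
4. State alpha and sidedness.
5. Reconcile the end-of-trial outcome wording, and the CMH primary analysis under Statistical Methods, with this choice.

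This takes a few lines of text, a small program change and no new data. The interval will be slightly wider, and a single-visit contrast may be a little less precise than an effect averaged over visits. Step 5 is more than an edit, because it fixes the time point and the test on which the primary claim rests.
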